6.1.3. Exploratory Endpoints

Version 2.0

[figure not shown]

[figure not shown]
6.1.3.6. Time to Death due to Respiratory Deterioration from Baseline up to Week 52

Events of death due to respiratory deterioration will be defined as adverse events with "Does this event represent a respiratory deterioration?" = "Yes" and with an outcome of "Fatal."

An analogous approach as described in Section 6.1.2.6 will be used to analyze this endpoint. If the number of event is rare at the end of the study, a listing will be provided instead of Kaplan Meier or Cox proportional hazard model.

Version 2.0

6.2. Extension Phase

6.2.1. Primary Efficacy Endpoint

The primary endpoints for the OLE Phase are 1) the change from OLE Baseline to Week 104 FVC % predicted, 2) the change from HZN-825 Baseline to Week 104 FVC% predicted.

Primary efficacy endpoint will be summarized for each visit in the OLE-SAF analysis set using descriptive statistics, presented by the treatment group subjects were randomly assigned to in the Core Phase.

A mixed model for repeated measures (MMRM) will be fit to the data for descriptive purposes using observed change in FVC % predicted values from all planned post-trial OLE Baseline assessments (Weeks 68, 80, 92 and 104). A similar model that was used in the Core Phase will be used for the Extension Phase. An unstructured covariance matrix will be used for the primary analysis; if the model does not converge, other covariance matrices will be considered. The least squares mean (LS mean) difference in change from OLE Baseline to Week 104 from MMRM will be estimated from this model. For subjects with missing data at 1 or more time points, the available data will be included in the analysis.

6.2.2. Exploratory Endpoints

The following exploratory endpoints for the OLE Phase will be summarized using descriptive statistics by treatment group subjects were randomly assigned to in the Core Phase in OLE-SAF analysis set. Continuous variables will be summarized with mean, standard deviation, median, quartiles and range. Categorical variables will be summarized with subject counts and percentages. Time to event variables will be presented with Kaplan-Meier plots and estimates.

104

- Change from both OLE and HZN-825 Baselines in proportion of subjects with decline in FVC % predicted ≥10% at Week 104
- Change from both OLE and HZN-825 Baselines in the 6MWT results to Week 104
- Change from both OLE and HZN-825 Baselines in K-BILD scores to Week 104
- Change from both OLE and HZN-825 Baselines in L-IPF scores to Week 104
- Change from both OLE and HZN-825 Baselines in LCQ scores to Week 104
- Time to first hospitalization due to respiratory distress from HZN-825 Baseline to Week
- Time to first onset of the composite endpoint of PFS from HZN-825 Baseline up to Week 104, where progression includes decline in FVC % predicted ≥10% from Baseline or death

Version 2.0

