This trial is designed to evaluate the efficacy and safety of fipaxalparant (HZN-825) in subjects with IPF. The trial will be conducted in 2 parts, Part 1 (Core Phase) and Part 2 (Extension Phase). In the Core Phase of the trial, subjects will receive fipaxalparant (HZN-825) 300 mg once daily (QD), fipaxalparant (HZN-825) 300 mg BID, or placebo during the 52-week Double-blind Treatment Period. Subjects who complete the Double-blind Treatment Period (Week 52) in the Core Phase may be eligible for the Extension Phase and will receive open-label fipaxalparant (HZN-825) 300 mg BID for 52 weeks (up to Week 104). This Extension Phase will allow subjects to have up to 24 months of treatment with fipaxalparant (HZN-825), as well as limit the duration subjects are exposed to placebo. The trial is designed with the Extension Phase to allow examination of long-term safety and tolerability of fipaxalparant (HZN-825), assessment of the durability of response and/or improved response in subjects who received fipaxalparant (HZN-825) in the Core Phase and evaluation of efficacy in subjects who received placebo in the Core Phase.

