## 9.3.2 Eligibility Criteria for the Extension Phase

## 9.3.2.1 Inclusion Criteria

Eligible subjects must meet/provide all of the following criteria:

- 1. Written informed consent.
- 2. Completed the Double-blind Treatment Period (Week 52) of the Core Phase of the trial; subjects prematurely discontinued from trial drug in the Core Phase of the trial for reasons other than safety or tolerability may be included at the discretion of the Investigator after completing scheduled visits, including Week 52 assessments.
- 3. Willing and able to comply with the prescribed treatment protocol and evaluations for the duration of the Extension Phase of the trial.

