#### 9.6.2 Extension Phase

### **9.6.2.1** Endpoints

Two types of Baseline are defined for the Extension Phase:

PRIVATE AND CONFIDENTIAL INFORMATION OF HORIZON THERAPEUTICS IRELAND DAC (A WHOLLY OWNED SUBSIDIARY OF AMGEN INC.)

Page 100 of 153

- OLE Baseline, defined as the latest measurement prior to the first dose of fipaxalparant (HZN-825) in Extension Phase
- Fipaxalparant (HZN-825) Baseline, defined as the latest measurement prior to the first dose of fipaxalparant (HZN-825) in either the Core Phase or the Extension Phase. For subjects who received placebo in the Core Phase, OLE Baseline will be the same as fipaxalparant (HZN-825) Baseline.

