1.1.2. Part 2 (Extension Phase)

The overall objective of the Extension Phase is to investigate the long-term efficacy, safety and tolerability of HZN-825, a selective antagonist of LPAR1, administered at a dose of 300 mg BID to subjects with IPF in a 52-week OLE following completion of the Core Phase of the trial. The dose for the Extension Phase may be modified based on the results of the Core Phase.

Two types of Baseline are defined for the Extension Phase:

- OLE Baseline, defined as the latest measurement prior to the first dose of HZN-825 in Extension Phase
- HZN-825 Baseline, defined as the latest measurement prior to the first dose of study drug (either HZN-825 or Placebo) in the Core Phase

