2.5. Changes from the Protocol Planned Analyses

The definition of HZN-825 Baseline has been updated from the protocol. This adjustment is essential to facilitate a comprehensive comparison of data over 104 weeks across all cohorts. As a result, HZN-825 Baseline has been redefined as the latest measurement prior to the first dose of study drug (either HZN-825 or Placebo) during the Core Phase.

For efficacy analysis, the prior use of IPF approved therapy will be used as a covariate in the mixed model for repeated measures instead of concomitant use of IPF approved therapy. In earlier protocol versions, the prior use of IPF approved therapy was used as a stratification factor, while concomitant use of IPF approved therapy was restricted. In protocol version 4, concomitant use of IPF approved therapy was permitted and used as a stratification factor. However, only a small number of enrolled subjects were on concomitant IPF therapy. To ensure a robust model estimate, the prior use of IPF approved therapy will be used in the model. Additional subgroup analysis will be conducted as needed, focusing on subjects who were on concomitant use of IPF approved therapy.

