3.1.4. OLE Phase Analysis Set

The OLE Phase Analysis Set (OLE-SAF) includes all subjects that are enrolled in OLE Phase and took at least 1 dose of study drug during the OLE Phase. This analysis set will be the

Version 2.0

primary analysis set for both efficacy and safety for the OLE Phase and combined periods. Subjects will be analyzed by actual treatment received in Core Phase.

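### The 104-week extension time-to-event curves start the clock at the first Core dose but include only subjects who reached Week 52 and took an open-label dose

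*SAP*

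**What the plan says.** SAP 6.2.2 presents the extension's time-to-event endpoints as Kaplan-Meier plots and estimates, by randomised Core group, in OLE-SAF. Two are legible: "Time to first onset of the composite endpoint of PFS from HZN-825 Baseline up to Week 104", and "Time to first hospitalization due to respiratory distress from HZN-825 Baseline to Week" 104.

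SAP 1.1.2 fixes the origin: "HZN-825 Baseline, defined as the latest measurement prior to the first dose of study drug (either HZN-825 or Placebo) in the Core Phase". SAP 2.5 declares this as a change from the protocol, made so that data can be compared over 104 weeks across all cohorts. SAP Table 1 applies it at Day 1.

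OLE-SAF (SAP 3.1.4) "includes all subjects that are enrolled in OLE Phase and took at least 1 dose of study drug during the OLE Phase". Extension entry requires a subject to have "Completed the Double-blind Treatment Period (Week 52) of the Core Phase of the trial" (Protocol 9.3.2.1). Early stoppers may enter at the investigator's discretion after the Week 52 assessments, but only if they stopped for reasons other than safety or tolerability. Protocol 9.3.2.2 also excludes subjects with an estimated life expectancy of 18 months or less.

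The protocol puts the placebo arm's origin elsewhere: "For subjects who received placebo in the Core Phase, OLE Baseline will be the same as fipaxalparant (HZN-825) Baseline" (9.6.2.1). Version 5.0, dated after SAP 2.0, keeps that rule.

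**The concern.** A Kaplan-Meier curve assumes that everyone in the risk set at a given time could have had the event at that time. Here membership is decided at about Week 52, but the clock starts at Week 0. Two things follow.

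- **Guaranteed survival.** Nobody in OLE-SAF can have died before entering the extension, so the death part of PFS is zero over that year by construction. Subjects who progressed or were hospitalised in the Core Phase and did not enter are missing too. FVC declines and hospitalisations in subjects who later entered are still counted.
- **Events before any drug.** In the placebo arm, a Core-year progression or hospitalisation is recorded as a first event from a baseline named after HZN-825, before the subject has taken any. A first-event analysis then ignores that subject's open-label year.

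The study report would also carry two different Week 52 PFS estimates for the same randomised arm. The Core analysis (SAP 6.1.2.7, in the FAS) counts the Core deaths and the extension curve cannot.

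**Working it through.** **1. Definitions side by side**

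| Item | Protocol 9.6.2.1 to 9.6.2.2 | SAP 1.1.2, 2.5, 3.1.4, 6.2.2 |
|---|---|---|
| Origin, two active arms | first Core dose | first Core dose |
| Origin, placebo arm | first extension dose | first Core dose (placebo) |
| Analysis set | Extension FAS: dosed entrants only | OLE-SAF: dosed entrants only |
| Delayed entry or landmark | none | none |
| Arms with guaranteed survival before entry | the two active arms | all three |
| Arms with events before any HZN-825 | none | placebo |

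The entrants-only problem is already in the protocol for the active arms. SAP 2.5 adds the placebo arm and the pre-drug events. There, 52 of the 104 weeks are off drug.

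**2. Size for PFS**

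The documents give no event rate, event count or entry rate for these endpoints, so there is no figure of the plan's to reproduce and every rate below is an assumption. Let p be the yearly probability of an FVC decline of at least 10, m the yearly mortality, and r the chance that a surviving progressor enters relative to a surviving non-progressor, all of whom enter. Hazards are constant and independent over both years.

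For p I take 20-30%. With the plan's SD of 9 and an assumed mean decline of 3 to 6 points, a normal distribution gives Φ((−10+3)/9) = 22% to Φ((−10+6)/9) = 33%. For m I take 5-15%.

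- All treated subjects: F52 = (1−p)(1−m); F104 = F52².
- OLE-SAF: S52 = (1−p)/[(1−p)+rp]; S104 = S52(1−p)(1−m).
- Share of counted events before Week 52: (1−S52)/(1−S104).

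Example with p = 0.20, m = 0.15, r = 1: F104 = (0.80×0.85)² = 0.462; S52 = 0.80; S104 = 0.80×0.80×0.85 = 0.544; difference 8.2 points.

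| p | m | r | F52 | S52 | F104 | S104 | Excess Wk 52 | Excess Wk 104 | Share before Wk 52 |
|---|---|---|---|---|---|---|---|---|---|
| 0.20 | 0.05 | 1 | 0.760 | 0.800 | 0.578 | 0.608 | 4.0 | 3.0 | 51% |
| 0.20 | 0.15 | 1 | 0.680 | 0.800 | 0.462 | 0.544 | 12.0 | 8.2 | 44% |
| 0.30 | 0.05 | 1 | 0.665 | 0.700 | 0.442 | 0.465 | 3.5 | 2.3 | 56% |
| 0.30 | 0.15 | 1 | 0.595 | 0.700 | 0.354 | 0.416 | 10.5 | 6.2 | 51% |
| 0.20 | 0.05 | 0.5 | 0.760 | 0.889 | 0.578 | 0.676 | 12.9 | 9.8 | 34% |
| 0.20 | 0.15 | 0.5 | 0.680 | 0.889 | 0.462 | 0.604 | 20.9 | 14.2 | 28% |
| 0.30 | 0.05 | 0.5 | 0.665 | 0.824 | 0.442 | 0.548 | 15.9 | 10.5 | 39% |
| 0.30 | 0.15 | 0.5 | 0.595 | 0.824 | 0.354 | 0.490 | 22.9 | 13.6 | 35% |

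Excess is in percentage points. Results for m = 0.10 lie between the rows. In the placebo arm, the last column is the share of counted events that precede any HZN-825.

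**3. Death alone, as an illustration**

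With yearly mortality m, two-year survival is (1−m)², while an entrants-only curve shows 1−m. For m = 5%, 10% and 15% that is 90%, 81% and 72% against 95%, 90% and 85%.

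No size was worked out for hospitalisation.

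**The case against.** The strongest defence is that the SAP made a declared choice for a reason. A common Day 1 origin puts the placebo-then-open-label arm beside the two active arms, the arms are shown separately, and this is a recognisable delayed-start display. The curves are exploratory and carry no test. Core deaths are not hidden, because Core PFS, hospitalisation and respiratory death have their own analyses. All of that stands, and it limits the consequence. It does not answer the selection problem: a comparison over 104 weeks is not served by a set whose members had to survive the first 52.

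The defence is also right to resist several stronger readings:

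- **That SAP 2.5 caused the whole problem, so restoring the protocol baseline would cure it.** Protocol 9.6.2.1 and 9.6.2.2 already combine a Core Day 1 origin with an entrants-only set in both active arms. Restoring that baseline repairs only the placebo arm.
- **That the death-only gaps of 5 to 13 points describe the planned curves.** No death-only curve is visible in SAP 6.2.2. The protocol lists respiratory death from the same origin, but that is not all-cause mortality.
- **That the protocol's 2 to 3 year median survival sets the size.** Under an exponential model it would give 71-79% shown against 50-63% true. But that median runs from diagnosis in general IPF, and this trial takes subjects up to 7 years from diagnosis, selected on FVC and DLCO.
- **That the extension cannot meet its aims.** Protocol 7.2 wants "evaluation of efficacy in subjects who received placebo in the Core Phase". Change in FVC % predicted from OLE Baseline (SAP 6.2.1) and the proportion with a decline of at least 10% from OLE Baseline (SAP 6.2.2) still inform it.
- **That every arm is certain to be overstated.** Subjects also fail to enter for safety or tolerability, so the net direction in each arm is expected, not proven.

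The endpoint lists in SAP 6.2.2 and Protocol 9.6.2.1.3 are partly redacted or broken, so only the legible endpoints are judged.

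**Conclusion.** The point holds as a mismatch between time origin and analysis set. It follows from the definitions and does not depend on any assumed rate. Death before about Week 52 is impossible in OLE-SAF, non-entrants' Core events are absent, and in the placebo arm Core-year events on placebo end follow-up for the endpoint before HZN-825 begins.

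The size does depend on assumptions. Under the rates above, PFS at Week 104 is overstated by about 2-8 points if all survivors enter and by 10-14 points if progressors are half as likely to enter. At Week 52 the gaps are 3.5-12 and 13-23 points. About 28-56% of counted events fall before Week 52. These figures assume constant, independent hazards and some Core deaths.

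The primary and key secondary Core inference and its alpha are untouched. This should be corrected before the extension analysis, but it is not a threat to the trial's main result.

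**What to change.** Amend SAP 6.2.2, and reconcile Protocol 9.6.2.1.3 and 9.6.2.2 with it:

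- **(a) Extension view.** In OLE-SAF, start each time-to-event endpoint at the first extension dose, measure FVC decline from OLE Baseline, and count only later events.
- **(b) 104-week view, if one is kept.** Use all Core FAS subjects from Day 1 by randomised arm and censor non-entrants at the end of their Core follow-up. State that this censoring may be informative, since sicker subjects may be less likely to enter.
- **(c) Label.** Call the SAP's origin Core Baseline, so that it is not confused with the protocol's baseline of the same name.

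Left truncation at the first extension dose is not a route to a 104-week curve: nobody would be at risk in Weeks 0-52, so it yields only the conditional estimate already given by (a).

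The cost is SAP and protocol wording and the reprogramming of a few descriptive figures. No new data are needed. The extension survival figures will probably look less favourable.

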7. SAFETY ANALYSES

Safety outcomes will be summarized descriptively for each study phase and combined periods. No inferential statistics are planned for safety outcomes. Safety analyses will be based on the Safety Analysis Set for the Core Phase, and OLE-SAF set for the OLE Phase and the combined periods.

7.1. Adverse Events and Deaths

7.1.1. Adverse Event Dictionary

Clinical and laboratory adverse events (AEs) will be coded using the current version of MedDRA. System organ class (SOC), high-level group term (HLGT), high-level term (HLT), preferred term (PT), and lower-level term (LLT) will be provided in the AE dataset.

7.1.2. Adverse Event Severity

Adverse events are graded by the investigator as Grade 1, 2, 3, or 4 according to the toxicity criteria specified in the protocol (Rheumatology Common Toxicity Criteria [RCTC] v2.0 (Woodworth T, 2007)). The severity grade of events for which the investigator did not record severity will be categorized as "missing" for tabular summaries and data listings. The missing category will be listed last in summary presentation.

7.1.3. Relationship of Adverse Events to Study Drug

Related AEs are those for which the investigator selected "Related" on the AE CRF to the question of "Relationship to Study Treatment". Relatedness will always default to the investigator's choice, not that of the medical monitor. Events for which the investigator did not record relationship to study drug will be considered related to study drug for summary purposes. However, by-subject data listings will show the relationship as missing.

7.1.4. Serious Adverse Events

Serious adverse events (SAEs) will be identified and captured as SAEs if the AEs met the definitions of SAEs that were specified in the trial protocol. SAEs captured and stored in the clinical database will be reconciled with the Horizon Global Safety database before data finalization.

7.1.5. Summaries of Adverse Events and Deaths

Treatment emergent adverse events (TEAEs) are defined as adverse events occurring or worsening after the first dose of trial drug through 28 days after the last dose. For those patients who entered OLE Phase, date of their first dose in OLE Phase marks the end of reporting period for Core Phase.

Version 2.0

Prior AEs are defined as any AE with a start date prior to the date of first dose of study treatment. Prior AEs will not be summarized, but will be included in listings.

7.1.5.1. Summaries of AE Incidence

The incidence of following AEs will be summarized by SOC, PT, and treatment group for each study phase and the combined periods. Number and percentage of subjects who experienced events will be reported. AE summaries followed by an asterisk(*) will include the number of events and the corresponding exposure adjusted incidence rate:

- 1 TEAEs*
- 2 RCTC Grade 3 or higher TEAEs*
- 3 Serious TEAEs*
- 4 Treatment-related TEAEs*
- 5 TEAEs by maximum severity
- 6 Treatment-related TEAEs by maximum severity
- 7 Serious treatment-related TEAEs*
- 8 TEAEs assessed by the investigator as representing respiratory deterioration*
- 9 TEAEs assessed by the investigator as IPF-disease related*
- 10 TEAEs leading to permanent withdrawal of any trial drug*
- 11 TEAEs leading to death (ie, outcome of death)*
- 12 Subject incidence of AESIs: Orthostatic hypotension

Additionally, the frequency of TEAEs occurring in > 5% of subjects in any treatment group, serious TEAEs occurring in >3% of subjects in any treatment group, treatment-related serious TEAES occurring in >=2% of subjects in any treatment group, will be summarized by treatment group, primary SOC, and preferred term.

Multiple events will be counted only once per subject in each summary of subject counts. Adverse events will be summarized and listed first in alphabetic order of SOC and then by PT in descending alphabetical order within each SOC. For summaries by severity, the most severe severity will be used for those AEs that occurred more than once in a given subject during the trial.

In addition to the above summary tables, TEAEs and treatment-related TEAEs will be summarized by PT only in descending order of total frequency.

Version 2.0

In addition, data listings will be provided for the following:

- All AEs, indicating whether the event is treatment emergent
- SAEs
- Treatment-related serious TEAEs and non-serious TEAEs
- Deaths
- AEs leading to permanent withdrawal of trial drug
- Adjudicated AEs
- Adverse events of special interest: Orthostatic hypotension

7.1.6. Adverse Events of Special Interest (AESI)

Orthostatic hypotension is the only AESI identified for this trial. Horizon will consider an event of orthostatic hypotension if the following definition is met: a reduction of systolic blood pressure by ≥ 20 mmHg or reduction of diastolic blood pressure by ≥ 10 mmHg at specific timepoints in the standing position and associated with symptoms such as lightheadedness, blurred vision, weakness, fatigue, cognitive impairment, nausea, palpitations, tremulousness, headache, presyncope or syncope.

Any spontaneously reported signs or symptoms possibly associated with orthostatic hypotension will be captured as AEs. These will be identified based on the flag within the dataset and/or programmatically using the standard MedDRA query (SMQ) search criteria.

Results of the corresponding orthostatic hypotension assessment (when performed) will be listed.

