# 9.5.5.5 Orthostatic Hypotension Assessment

Due to a potential role of LPA in vascular tone (Section 7.1.2), orthostatic hypotension will be assessed at the time points indicated in Section 2.1 and Section 2.2.

BP and heart rate will be measured after the subject has rested ≥5 minutes in the supine position and after 1 minute and 3 minutes in the standing position, as per the Orthostatic Hypotension Assessment Manual provided by the Sponsor. See Section 9.5.5.1.1.4 for more information on orthostatic hypotension assessment.

A copy of the Orthostatic Hypotension Assessment Manual is provided in Section 17.9.

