# 9.6.1.6 Safety and Tolerability Analyses

All subjects who receive at least 1 dose or partial dose of trial drug will be included in safety and tolerability analyses. Subjects who receive treatment other than that to which they were randomized will be included in summaries with the treatment received. Subjects who receive more than 1 treatment will be listed separately and included in summaries with the treatment received most frequently.

The number and percentage of subjects reporting at least 1 TEAE, SAE, AESI, and TEAE resulting in premature discontinuation of trial drug for each unique System Organ Class (SOC) and Preferred Term will be summarized. AE rates (events per patient-year of follow-up during dosing) will also be summarized to account for the different treatment durations. TEAEs and SAEs will also be summarized by severity and relationship to trial drug as assessed by the Investigator. Grade 3 and above TEAEs will also be summarized for each unique SOC and Preferred Term. Orthostatic hypotension is prospectively defined as an AESI and will be summarized separately.

Summary statistics will be used for laboratory values, vital signs, ECG results, and use of concomitant medications.

No inferential statistics are planned for any safety endpoint.

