### Orthostatic Hypotension Assessment Manual

## Safety Vital Signs (Supine and Orthostatic) Per Protocol

Information about the orthostatic hypotension assessment and its intended use:

- This assessment is purposed to inform whether treatment with HZN-825 is associated with orthostatic hypotension. This assessment is part of the overall safety evaluation of the current protocol.
- 2. This data is being collected as part of the overall safety analysis for the current trial.

The supine and orthostatic vital signs, as outlined in the protocol along with safety assessments, will be performed using either a standard manual or automated blood pressure cuff. A single measurement will be captured at each of the timepoints as indicated in the protocol and reviewed accordingly. For this assessment, heart rate and systolic and diastolic blood pressure will be measured after 5 minutes in supine resting position followed by measurement after 1 minute and 3 minutes in the standing position.

Positive orthostatic hypotension test is defined as the combination of a reduction of systolic blood pressure by  $\geq 20$  mmHg or reduction of diastolic blood pressure by  $\geq 10$  mmHg, and the presence of one or more of the following associated clinical symptoms:

 lightheadedness, blurred vision, weakness, fatigue, cognitive impairment, nausea, palpitations, tremulousness, headache, presyncope or syncope

If positive for orthostatic hypotension, as defined above (inclusive of clinical symptoms), the subject should be assisted to lie back down in the supine position and monitored for clinical resolution of symptoms.

Prior to beginning the procedure, patients should be instructed to report any symptoms experienced throughout the assessment without probing for specific types of adverse events. If any symptoms occur during the assessment in combination with the blood pressure reductions noted above, they are considered as part of the orthostatic hypotension event and will not be recorded separately as individual adverse events.

If above symptoms are reported by the patient throughout the assessment, without the blood pressure reductions noted above, then the symptoms will only be recorded separately as adverse events if they meet any of the criteria below, and orthostatic hypotension will not be recorded.

- The symptoms are severe and/or require medical interventions

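### The SAP plans no by-arm summary of the supine-to-standing blood pressure change, or of threshold falls regardless of symptoms, in the trial's orthostatic assessment

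*SAP*

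**What the plan says.** The Orthostatic Hypotension Assessment Manual (Protocol 17.9) states the aim: "This assessment is purposed to inform whether treatment with HZN-825 is associated with orthostatic hypotension". Under Protocol 9.5.5.5, blood pressure and heart rate are measured supine and then "after 1 minute and 3 minutes in the standing position". Protocol 9.5.5.1.1.4 and the schedule in 2.1 place this in the Core Phase on Day 1 and at Weeks 4, 28 and 52 (or premature discontinuation). It is repeated in the Extension Phase.

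On output, SAP 7.1.6 says: "Results of the corresponding orthostatic hypotension assessment (when performed) will be listed". The by-arm orthostatic output is item 12 of SAP 7.1.5.1, "Subject incidence of AESIs: Orthostatic hypotension". Protocol 9.6.1.6 agrees: "Orthostatic hypotension is prospectively defined as an AESI and will be summarized separately".

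That event needs two things. SAP 7.1.6 requires a fall of at least 20 mmHg systolic or 10 mmHg diastolic "at specific timepoints in the standing position and associated with symptoms such as lightheadedness" and others. The manual builds its positive test the same way: "Positive orthostatic hypotension test is defined as the combination of a reduction of systolic blood pressure" or of diastolic pressure, together with at least one symptom. For spontaneously reported signs and symptoms possibly linked to orthostatic hypotension, SAP 7.1.6 says: "These will be identified based on the flag within the dataset and/or programmatically using the standard MedDRA query (SMQ) search criteria". That search runs on reported events and not on the measured pressures.

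**The concern.** A listing does not answer a between-arm question. A subject whose pressure falls past the threshold on standing but who volunteers no symptom enters no planned table, unless the investigator happens to report the fall as an ordinary adverse event. The average postural change in each arm is not tabulated either.

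Three features of this trial make that worth correcting:

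- Orthostatic hypotension is the only adverse event of special interest. Protocol 7.1.3.5 names it an important potential risk and reports it, with postural dizziness, as slightly more frequent on drug than on placebo in the data to date.
- The manual tells sites not to probe for particular symptoms, so the symptom half of the definition depends on what subjects volunteer.
- Protocol 7.3 expects the two regimens to differ about 2-fold in AUC and about 6-fold in trough concentration, so a gradient across arms in postural pressure is a natural thing to look at.

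The SAP already tabulates objective thresholds by arm, whatever the symptoms, for liver tests (7.2.2) and QTcF (7.5.2).

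**Working it through.** The plan states no figure on this point, so the check is of planned outputs, followed by the size of what is left out.

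**Step 1. Look for any by-arm output that uses the postural readings.**

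| Place | What it gives | Supine-to-standing change, or threshold count regardless of symptoms? |
|---|---|---|
| SAP 7.1.5.1, item 12 | Incidence of the event of special interest | No; symptoms required |
| SAP 7.1.6 | Listing of assessment results | No |
| SAP 7.3 | Observed value and change from Baseline per vital sign, and a shift table | No; no postural parameter named |
| SAP 7.6 | Echocardiograms | No |
| SAP 8 | No further analyses | No |
| SAP 2.2 | Blinded safety reviews, arms pooled | No |
| Protocol 9.6.1.6 and 9.6.2.4 | Adverse event summaries; vital signs summaries | No |

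The count of such outputs is 0. On SAP 7.3, Protocol 9.5.5.4 takes routine blood pressure seated, and Protocol 9.5.5 names vital signs and the orthostatic assessment as separate safety variables.

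**Step 2. Count the readings concerned.** Inputs: 135 subjects, 45 per arm (SAP 1.3). Of the four Core Phase assessments, Day 1 is pre-dose (Protocol 2.1, footnote 2), which leaves three post-baseline: Weeks 4, 28 and 52.

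- Assessments per arm: 45 × 3 = 135.
- All arms: 135 × 3 = 405.
- Standing readings, two per assessment: 405 × 2 = 810.

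These are maxima under full attendance.

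**Step 3. Precision of the missing table.** The documents give no rate of falls past the threshold, so the rates below are assumptions. For rates p0 and p1 at 45 per arm, SE = √[p0(1−p0)/45 + p1(1−p1)/45], and the 90% half-width is 1.645 × SE. The 90% level follows the plan's 10% two-sided level.

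| Assumed rates | Difference (points) | SE (points) | 90% half-width (points) |
|---|---|---|---|
| 5% vs 15% | 10 | √(0.0475/45 + 0.1275/45) = 6.2 | 10.3 |
| 10% vs 20% | 10 | √(0.09/45 + 0.16/45) = 7.5 | 12.3 |
| 10% vs 30% | 20 | √(0.09/45 + 0.21/45) = 8.2 | 13.4 |
| 20% vs 40% | 20 | √(0.16/45 + 0.24/45) = 9.4 | 15.5 |

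A 10-point difference would have an interval that includes zero in both cases shown. A 20-point difference would not.

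**The case against.** **The listing sentence may be about something else.** It follows the paragraph on spontaneously reported symptoms, and its wording about a corresponding assessment, when performed, could mean the extra work-up that Protocol 9.5.5.1.1.4 asks for when clinically indicated. This is a fair reading. It does not help the plan: if the sentence does not cover the scheduled readings, SAP 7.1.6 gives them no output at all.

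**SAP 7.3 may cover the readings.** The manual's own heading calls them safety vital signs, and SAP 3 refers presentation details to a TLF document that is not available here. So a reader should not conclude that the supine and standing values are certain to appear in a listing and nowhere else. Even under that reading, 7.3 gives each parameter's change from Baseline. It gives neither the fall on standing nor a count past the threshold, and 7.1.6 does not defer the matter to the TLF document.

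**The stated purpose is already met.** The manual defines a positive test as a fall plus symptoms, and that event is summarised by arm. This stands in part: it would be wrong to infer that orthostatic hypotension is never compared between arms. What is missing is falls without symptoms and the size of the change.

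**The symptom-recording rules.** A reader may notice that Protocol 9.5.5.1.1.4 gives inconsistent rules for recording symptoms, and infer that the event count is unreliable. The inconsistency concerns symptoms without a pressure fall. For symptoms with a fall the rule is uniform, so the count is not affected.

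**The readings are not ideal data.** Each time point is a single cuff measurement. The manual has a subject who tests positive helped back to supine, so the 3-minute reading may be missing, and visits can be missed. The readings are objective but cannot be called complete.

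**Conclusion.** The gap is real and small. No planned output gives, by treatment group, the supine-to-standing change or the proportion past the 20/10 mmHg threshold regardless of symptoms. This holds on either reading of the listing sentence and even if SAP 7.3 is stretched to cover the readings. It rests on the SAP text, since the TLF shells could not be seen. Up to 405 post-baseline Core Phase assessments are concerned, assuming 135 subjects and full attendance.

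No estimate, test or decision rule in the plan changes. Nor do the documents support expecting the missing table to establish a drug effect: the manual speaks of association, SAP 7 plans no safety inference, and under the assumed rates the 90% half-widths run from about 10 to 15.5 points. The gain is a by-arm and by-dose description of a recognised potential risk from data already collected.

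**What to change.** In SAP 7.1.6, keep the listing and add a descriptive table by treatment group and visit, with the pre-dose Day 1 assessment as Baseline, showing:

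- the number and percentage of subjects with a systolic fall of at least 20 mmHg or a diastolic fall of at least 10 mmHg from supine at 1 or 3 minutes, split by with and without symptoms;
- the number and percentage with any such post-baseline occurrence;
- descriptive statistics for the supine-to-standing change in systolic and diastolic pressure.

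Count a subject as meeting the threshold if either standing reading does, because the 3-minute reading may be missing after a positive 1-minute reading. State the number assessed at each visit as the denominator.

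The cost is one or two extra tables from data already collected. They will be imprecise and should be labelled descriptive. No visit, dose, measurement or clinical rule changes.
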